3.4.2. HRQoL Endpoints

- Scores and change from baseline at Weeks 12, 32 (UC-PRO only), and 52 in the following:
 - Two Ulcerative Colitis Patient-Reported Outcomes (UC-PRO) modules. UC-PRO scoring is derived by calculating the average using at least 4 out of 7 daily scores, using the visit date to determine the days to be used. UC-PRO is available on the participants eDiary 14 days prior to and 14 days after the projected visit date. Participant should complete UC-PRO when it becomes available on the device for the visit, continuing until the visit occurs.
 - UC-PRO Signs and Symptoms (UC-PRO/SS). It is a 9-item questionnaire containing 2 domains: Bowel movement signs and symptoms (6 items) and functional symptoms (3 items). An average score is calculated for each domain; a higher score indicates worse symptoms.
 - UC-PRO Systemic Symptoms. The Systemic Symptoms measure includes 5 items, scored as a single scale, to address the presence and severity of systemic symptoms including pain, feeling tired, lack of appetite, feeling weak, and thirst.
 - Functional Assessment of Chronic Illness Therapy-Fatigue (FACIT-F). It is a 13-item fatigue instrument utilized to assess fatigue/ tiredness and its impact on daily activities and functioning in a number of chronic diseases. The instrument includes items such as tiredness, weakness, listlessness, lack of energy, and the impact of these feelings on daily functioning (eg, sleeping, and social activities).
 - Work Productivity and Activity Impairment Questionnaire Ulcerative Colitis (WPAI-UC). It consists of 6 questions asking about the effect of UC on the participant's ability to work and perform regular activities. The percent work time missed due to problem (absenteeism), percent impairment while working due to problem (presenteeism), percent overall work impairment due to problem, and percent activity impairment due to problem are derived on the eCRF directly. Details about derivation can be found in Section 9.2.1.
 - Urgency numeric rating scale (NRS). It is a single item that measures the severity for the urgency (sudden or immediate need) to have a bowel

- movement in the past 24 hours using an 11-point NRS ranging from 0 (no urgency) to 10 (worst possible urgency).
- Inflammatory Bowel Disease Questionnaire total score (IBDQ). It is a 32item self-administered questionnaire which has 4 dimensions: bowel
 symptoms (10 items), systemic symptoms (5 items), emotional health (12
 items), and social function (5 items). Responses are graded on a 7-point
 Likert scale where 7 denotes "not a problem at all" and 1 denotes "a very
 severe problem". Scores range from 32 to 224, a higher score indicates better
 quality of life. Details about scoring rules for IBDQ total score and 4 domain
 subscores can be found in Section 9.2.2.
- Medical Outcomes Study 36-Item Short Form Health Survey, version 2 physical and mental component and domain scores (SF-36). The 36-Item Short Form Health Survey (SF-36) is a 36-item, participant-reported survey of participant health. The SF-36 consists of 36 questions measuring 8 health domains: Physical functioning, bodily pain, role limitations due to physical problems, role limitations due to emotional problems, general health perceptions, mental health, social function, and vitality. The participant's responses are solicited using Likert scales that vary in length, with 3 to 6 response options per item. The SF-36 will be scored using 2 overall summary scores: Physical component summary and mental component summary scores. A higher score indicates better health status. Details about scoring rules and derivations of domain scores can be found in Section 9.2.3
- Patient Global Impression of Change (PGIC). It is the PRO counterpart to the Clinical Global Impressions (CGI) scale, which was published in 1976 by the National Institute of Mental Health (US). It consists of one item taken from the CGI and adapted to the patient.
- UC-related hospitalizations.
- UC-related surgeries, including colectomy.

3.4.3. Efficacy-Related Biomarkers Endpoints

- Change from baseline in level of fecal calprotectin at Weeks 2, 4, 8, 12, 24, and 52.
- Change from baseline in level of high-sensitivity C-reactive protein (hs-CRP) at Weeks 2, 4, 8, 12, 16, 24, 32, 48, and 52.
- Change and percentage change from baseline in lymphocyte counts at Weeks 2, 4, 8, 12, 16, 24, 32, 48, and 52.

3.5. Baseline Variables

Unless otherwise specified, baseline is defined as the last non-missing measurement taken prior to the first dose (including unscheduled assessments). If measurements include time

(except for health-related quality of life instruments), the date/time will be used to define Baseline. Otherwise, only dates will be compared. For health-related quality of life instruments, only the date will be used to derive Baseline. In the case where the last nonmissing measurement and the date of first dose coincide and time is not collected, if the measurement was planned in the protocol to be done prior to the date of first dose, that measurement will be considered in defining Baseline.

Regarding cardiac analyses, for the analysis of hHR endpoints in Section 3.3.2, the last predose hHR as derived by the cardiac central laboratory from Holter recording will be used as the baseline measurement (which may be based on recording from a partial hourly interval; see derivation of hourly timepoint in Section 9.1.7), except in the analysis of time to nadir hHR by baseline ECG HR, where baseline mean heart rate from pre-dose 12-lead ECG will be used.

The following demographic data and Baseline characteristics will be summarized:

- Age on consent (years)
- Sex
- Race
- Ethnicity
- Woman of childbearing potential (Yes or No)
- Height (cm)
- Weight (kg)
- Body mass index (BMI) (kg/m²)
- Alcohol consumption (Yes or No)
- Caffeine consumption (Yes or No)
- Tobacco use (Yes or No)
- Region (North America, Western Europe, Easter Europe, Other)

The following Baseline characteristics related to UC will be summarized:

- Baseline MMS
- Baseline RB subscore
- Baseline SF subscore
- Baseline ES

- Baseline Physician's Global Assessment (PGA)
- Baseline TMS
- Duration of UC (years)
- Any acute exacerbations within past 12 months (Yes, No, Ongoing), including the number of acute exacerbations among those with any acute exacerbation = Yes
- Colonoscopy within past 12 months (Yes or No)
- Surgery for UC (Yes or No), including the number of surgeries
- Hospitalizations for UC (Yes or No), including the number of hospitalizations
- Naïve to biologic or JAK inhibitor therapy (Yes or No) Reported (used for stratification at randomization)
- Naïve to biologic or JAK inhibitor therapy (Yes or No) Actual (medications reported on the eCRF)
- Baseline corticosteroid use (Yes or No) Reported (used for stratification at randomization)
- Baseline corticosteroid use (Yes or No) Actual (medications reported on the eCRF)
- Naïve to biologic or JAK inhibitor therapy Difference between the Reported and the Actual
- Baseline corticosteroid use (Yes or No) Difference between the Reported and the Actual
- Prior failure of oral 5-ASA only (Yes or No)
- Prior failure of anti-TNF α (Yes or No)
- Prior failure of anti-TNF α or vedolizumab (Yes or No)

Additional baseline characteristics related to UC can be added, if deemed needed.

Prior treatment

Prior treatment for UC will be summarized, including category of treatment, reason for discontinuation, and estimated duration (weeks) of corticosteroid use over the last 12 months.

Medical history

Medical history will be collected on the medical history eCRF and coded using Medical Dictionary for Regulatory Activities (MedDRA, v26.1). The version used to code medical history will be displayed in the outputs.

4. ANALYSIS SETS (POPULATIONS FOR ANALYSIS)

Data for all participants will be assessed to determine if participants meet the criteria for inclusion in each analysis set prior to unblinding the database and classifications will be documented per standard operating procedures. The description of each analysis set is provided in Table 5 below.

Table 5. Summary of Analysis Sets

Analysis Set	Description			
Screened Set	The Screened Set will consist of all participants who sign informed consent to participate in the study.			
Randomized Set	The Randomized Set will consist of all participants who are randomized to study treatment.			
Full Analysis Set (FAS)	The FAS will consist of all randomized participants, who receive at least 1 dose of study treatment. Under this approach, participants will be summarized by the treatment group to which they were randomized, regardless of the treatment actually received during the study.			
Primary Analysis Set (PAS):	The Primary Analysis Set will consist of participants in FAS with baseline MMS 4-6, baseline ES \geq 2 and baseline RB score \geq 1. This analysis set will be the primary analysis set for analyses of all efficacy endpoints.			
Modified Primary Analysis Set (mPAS)	The mPAS will consist of all participants in PAS, who receive at least 1 dose of study treatment and have a baseline and at least 1 post-randomization measurement. Under this approach, participants will be summarized by treatment to which they were randomized, regardless of the treatment received during the study. Note that the mPAS can vary with endpoints since some participants may have the needed data for inclusion in the mPAS for some endpoints but others may not.			
Safety Set	The Safety Set will include all randomized participants who receive at least 1 dose of study treatment. For this set, participants will be analyzed according to the treatment received, regardless of randomization. The Safety Set will be used for all safety analyses			
Modified Safety Set	The Modified Safety Set will include all participants who receive at least 1 dose of study treatment and have Holter recording data on Day 1. Unless stated otherwise, the analyses of Cardiac Holter endpoints (Section 3.3.2) will be performed for the Modified Safety Set. For this set, participants will be analyzed according to the treatment received, regardless of randomization.			
Pharmacokinetic Set	The Pharmacokinetic Set will include all participants in the Safety Set with at least 1 quantifiable postdose etrasimod concentration which is not impacted by protocol violations or events with potential to affect the etrasimod concentration.			

5. GENERAL METHODOLOGY AND CONVENTIONS

5.1. Hypotheses and Decision Rules

There are multiple null hypotheses for the comparison of etrasimod 2 mg versus placebo for the following primary endpoint and key secondary efficacy endpoints. The family-wise typeI error rate will be controlled at the level of 0.05 using the fixed sequential testing approach in the order specified below.

- (1) Clinical remission at Week 52 (Primary efficacy endpoint)
- (2) Endoscopic improvement at Week 52
- (3) 12-week corticosteroid-free clinical remission at Week 52
- (4) Clinical remission at Week 12
- (5) Endoscopic improvement at Week 12
- (6) Sustained clinical remission (clinical remission at both Week 12 and Week 52)
- (7) Histologic-Endoscopic Mucosal Improvement at Week 52
- (8) Complete symptomatic remission at Week 52
- (9) Complete symptomatic remission at Week 12

Hypotheses for all other efficacy endpoints not described above are to be tested at the nominal 5% (2-sided) significance level, without adjusting for multiple comparisons.

5.2. General Methods

In general, for descriptive analyses, number and percent will be presented for binary variables. Number, mean, standard deviation, median, minimum, maximum, first and third quartiles will be presented for continuous variables.

The general considerations for data derivation details can be found in Section 9.1 Data Derivation Details of Section 9. Appendix, such as derivations for some demographics and baseline characteristics related variables (Section 9.1.1), reference start date and study day (Section 9.1.2), retests, unscheduled visits, and early termination data (Section 9.1.3), definition and use of visit windows in reporting (Section 9.1.4), etc.

5.2.1. Analyses for Binary Efficacy Endpoints

The primary analysis of all binary efficacy endpoints will be performed based on the Mantel–Haenszel (MH) weighted method, stratified by (a) naïve to biologic or JAK inhibitor therapy at study entry (yes or no) and (b) baseline corticosteroid use (yes or no). Results will be presented as the number of participants with response, proportion of participants with response, estimated common risk difference and associated two-sided 95% confidence intervals (CIs), and p-values from the MH weighted method.

For (a) and (b) mentioned above that are used in MH weighted method, the reported strata (which are based on randomization system) will be used for the statistical analyses. Analyses may be repeated using actual strata (which are based on medications reported in eCRF) if the strata data recorded in the randomization system and the actual strata data recorded in the

CRF are inconsistent for more than 10% of the randomized participants. i.e., if there are more than 10% of randomized participants whose reported strata are not the same as actual strata.

The methods for handling with missing data are described in Section 5.3 below.

5.2.2. Analyses for Continuous Non-Cardiac Endpoints

All continuous exploratory efficacy endpoints, HRQoL endpoints and efficacy-related biomarker endpoints measured longitudinally will be summarized by visit using descriptive statistics (n, mean, standard deviation [SD], median, minimum, and maximum), and presented in a listing. They will also be analyzed using a linear mixed-effect model, with factors for naïve to biologic or JAK inhibitor therapy at study entry (yes or no), baseline corticosteroid use (yes or no), treatment, visit, treatment by visit interaction and baseline value. Reported strata will be used in the model. Unstructured covariance will be used. If there is a convergence issue in fitting the unstructured covariance, other covariance structures, such as a compound symmetry covariance structure will be considered as appropriate. LSM for each treatment group, standard errors (SEs), LSMs in treatment difference and associated 95% CIs, and p-values by visit will be reported.

Analyses above based on linear mixed-effect model may be repeated using actual strata if mis-classification occurs in more than 10% of randomized participants. i.e., if there are more than 10% of randomized participants whose reported strata are not the same as actual strata.

5.2.3. Analyses for Cardiac Endpoints

For binary cardiac endpoints, data will be summarized using descriptive statistics, including number of participants (n), percentage, and 2-sided 95% Clopper-Pearson CI. No missing data will be imputed.

For continuous cardiac endpoints, data will be summarized using descriptive statistics, including number of participants (n), mean, median, SD, 2-sided 95% CI, first quartile (Q1), third quartile (Q3), minimum, and maximum by timepoint. No missing data will be imputed.

For count cardiac endpoints, data will be summarized using the same descriptive statistics as for continuous endpoints. No missing data will be imputed.

5.3. Methods to Manage Missing Data

5.3.1. Binary Efficacy Endpoints

Participants with a missing binary efficacy outcome will be included in the analyses using the following method:

- Primary method: participants with missing data will be treated as nonresponders.
- Other methods for sensitivity analyses:
 - 1) Multiple imputation under missing at random (MAR) assumption.

- 2) Tipping point analysis.
- 3) multiple imputation with Copy Reference (CR) under missing not at random (MNAR) assumption.
- 4) Hybrid imputation with multiple imputation to handle missing endoscopy data due to the COVID-19 pandemic impact and Ukraine war impact, nonresponder imputation (NRI) for missing data not due to the COVID-19 pandemic impact and Ukraine war impact.

More details are provided in Sections 5.3.1.1 and 5.3.1.2 below.

5.3.1.1. Primary Missing Data Handling Method

For binary efficacy endpoints, participants having any of intercurrent events 1) discontinue the study treatment during the double blind treatment period for any reasons, or 2) initiate a rescue medication for UC, or 3) have an increase in dose over Baseline levels in their existing UC medication, or 4) have a rescue non-drug treatment (eg, colectomy, ileostomy, or sigmoidectomy) during the study will be considered as nonresponders, that is, have a known outcome of nonresponse at any applicable timepoints.

For primary analysis, all participants with missing data for other reasons will be treated as nonresponders. That is, all missing data will be treated as nonresponse regardless of reasons.

5.3.1.2. Sensitivity Missing Data Handling Methods

Other methods of handling missing data will be applied for primary and key secondary efficacy endpoints, which are all binary, assuming different missing mechanisms: multiple imputation under MAR assumption, tipping point analysis, and copy to reference under MNAR assumption. The analyses based on these methods will all be performed for PAS only.

5.3.1.2.1. Multiple Imputation Under MAR Assumption

Missing data (eg, component scores of MMS at the planned assessment timepoints) will be imputed under the MAR assumption. Binary endpoints will subsequently be computed from observed and imputed data and analyzed using the same method as in the primary endpoint analysis for each imputed dataset. Then the results will be combined using multiple imputation methodology (Rubin, 1987 Section 8 References).

The following steps will be implemented:

Step 1

Regardless of the arbitrary missing data pattern (ie, non-monotone or monotone), a fully conditional specification (FCS) method with predictive mean matching for continuous variables will be used to impute the missing data at all timepoints. The FCS method allows for separate conditional distributions for each imputed variable. The predictive mean matching approach creates a regression model using parameters sampled from the posterior distribution and then a predicted value for each missing value is computed. The missing

value is replaced by randomly selecting an observation from a set of 'k' values that are the closest predicted values to the missing predicted value. Missing data imputation will be performed using the SAS PROC MI procedure (SAS Software v9.4. SAS Institute Inc, Section 8 References). The number of imputations will be 40. A separate imputation model will be used for each treatment group. The RB subscore, SF subscore, ES, PGA, stratification variables, a binary variable indicating if a participant is a prior UC treatment failure of oral 5-ASA only (ie, participant had an inadequate response, loss of response, or intolerance to previous treatment with oral 5-ASA and did not have an inadequate response, loss of response, or intolerance to any other previous UC medication), Geboes index score, and biomarker measurements (absolute lymphocyte count [ALC], fecal calprotectin [FCP], hs-CRP, log-transformed) at each planned visit will be included in the imputation models. The random seed **8238946** will be used.

Step 2

For each of the imputed datasets at Week 12 and Week 52, participants will be classified as responder or nonresponder. For each dataset, the proportion of responders will be calculated. For endpoints requiring MMS, MMS will be recomputed by summing the scores of ES, SF, and RB.

Step 3

The MH weighted method, stratified by naïve to biologic or JAK inhibitor therapy at study entry (Yes or No) and baseline corticosteroid use (Yes or No) will be run for each of the 40 imputed datasets to obtain 40 estimators of interest at Week 12 and Week 52.

Step 4

Use Rubin's rule and SAS PROC MIANALYZE (Rubin, 1987; SAS Software v9.4. SAS Institute Inc Section 8 References) to produce an overall pooled estimate (mean of 40 estimates) with its associated SE, CI and p-value.

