At the end of the 12-Week Treatment Period, participants will undergo the Week 12 efficacy and safety assessments and procedures. Participants whose UC condition in the opinion of

the Investigator is stable or improving compared with baseline (Week 0/Day 1) will continue with their double-blind treatment and move into the 40-Week Treatment Period.

[figure not shown]
End of 40-Week Double-Blind Treatment Period (Week 52)

At the end of the 40-Week Treatment Period (ie, Week 52) and following completion of all study procedures, participants will have the option to enter into the Open-Label Extension (OLE) study (Study APD334-303) provided they meet all eligibility criteria. Participants who do not participate in the OLE study will have 2-Week and 4-Week Follow-Up visits after their last treatment administration.

Open-Label Extension Study [Study C5041012 (APD334-303)]

Participants whose UC condition in the opinion of the Investigator has not improved or has worsened, compared with baseline (Week 0/Day 1), may be eligible to enroll in the OLE study. Participants must complete Week 12 to be considered for the OLE study. Disease worsening will continue to be monitored by Investigators through the 40-Week Treatment Period (ie, from Weeks 13 to 52). Participants who either experience disease worsening in the 40-Week Treatment Period or complete all study procedures at Week 52 will have the option to enroll into the OLE study if they meet all eligibility criteria.

Figure 1. Study Design

Based on a 2-group Fisher's exact test, a two-sided significance level of 0.05, and a 2:1 randomization ratio, approximately 183 subjects (122 etrasimod, 61 placebo) are required to achieve at least 80% power to detect a difference of 20% in the primary endpoint of clinical remission (based on MMS) at Week 52 between the etrasimod treatment group (34%) and the placebo treatment group (14%). Alternatively, based on the same assumptions, using normal approximation to the binomial distribution, a two-sided test would achieve at least 90% power. The assumptions are based on the final analysis results in the Phase 3 Studies APD334-301 and APD334-302. Sample size is calculated using the EAST® software.

Based on the updated inclusion criteria in Protocol C5041011 (APD334-210) amendment 2.0, approximately 45 participants among the already randomized participants (assuming

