approximately 2:1 ratio of etrasimod:placebo) did not meet the amended Inclusion Criterion 5, which includes ES score ≥ 2 and RB score ≥ 1 . As a result, these participants will be excluded from the Primary Analysis Set (Section 4). Therefore, approximately 225 total participants (150 etrasimod, 75 placebo) were required to be enrolled into study C5041011 (APD334-210) under Protocol amendment 2.0.

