3.4. Other Endpoints

3.4.1. Exploratory Efficacy Endpoints

- Symptomatic remission at each study visit (Weeks 2, 4, 8, 12, 16, 24, 32, 40, 48, and 52). Two symptomatic remission derivations described in Section 3.2.1 will be applied, respectively.
- Symptomatic response at each study visit (Weeks 2, 4, 8, 12, 16, 24, 32, 40, 48, and 52). Symptomatic response is defined as ≥ 30% decrease from baseline in composite RB and SF subscores. Its derivation will be based on the following 2 approaches, respectively.
 - Symptomatic response 1, based on RB and SF derivation per protocol (Derivation 1, Section 3.1.1)
 - Symptomatic response 2, based on RB and SF derivation per FDA
 Draft Guidance (Derivation 2, Section 3.1.1)
- Clinical remission at Week 52 among participants achieving clinical response at Week 12. Three derivations for clinical remissions described in Section 3.1.3 will be applied, respectively.
- Reduction from baseline in both ES and RB or in both ES and SF at Week 52.
 Derivation 1 and 2 for RB and FS in Section 3.1.1 will be applied, respectively.
- Clinical response based on total Mayo score (TMS) at Week 52. The TMS includes all four components (ES, RB, SF and PGA) of the MCS. The total score range of the TMS is from 0 to 12 with each component ranging from 0 to 3 (0 = normal, 1 = mild, 2 = moderate, 3 = severe) and higher scores indicating more severe disease. Clinical response based on TMS is defined as a ≥ 3-point and ≥ 30% decrease from baseline in TMS, and a ≥ 1-point decrease from baseline in RB subscore or an absolute RB subscore ≤ 1. The TMS will be derived based on each of derivations for RB and SF (as defined in Section 3.1.1), respectively.
 - TMS clinical response 1, based on RB and SF derivation per protocol (Derivation 1, Section 3.1.1)
 - TMS clinical response 2, based on RB and SF derivation per FDA Draft Guidance (Derivation 2, Section 3.1.1)

- Histologic response based on Geboes Grading System at Week 52.
- Histologic remission based on the Geboes Grading System at Week 12. Histologic remission based on the Geboes Grading System is define as Geboes Score (GS) \leq 2.0
- Histologic remission based on the Geboes Grading System at Week 52
- Histologic response based on the RHI at Week 52.
- Histologic remission based on the RHI at Week 12. Histologic remission based on RHI is defined as a RHI score ≤ 3 with lamina propria neutrophils subscore = 0 and neutrophils in epithelium subscore = 0

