5.3.1.2.3. Copy Reference (CR) Multiple Imputation Under MNAR Assumption

Missing data will also be explored assuming an MNAR approach. MNAR assumes the missing values depend on unobserved outcomes even after accounting for the observed data. Therefore, participants cannot be modelled based on participants with observed data, and more assumptions are needed. Copy Reference approach (Carpenter et al, 2013) will be used. It is a type of missing data handling approach, assuming MNAR, where each missing value of MMS subscores for participants in the treatment group will be imputed using observed MMS subscores in the placebo group, and missing values of MMS subscores for participants in the placebo group will be imputed under the MAR approach. Once the missing MMS subscores are imputed, all binary efficacy endpoints (based on MMS) will be derived based on observed and imputed MMS subscores and analyzed using the same method described in Section 5.2.1 for each imputed dataset. Then the results will be combined using multiple imputation methodology based on the Rubin's rule. The random seed 8238946 will be used.

Step 1

Step 1 (a)

Intermittent missing data (before discontinuation from study) at each scheduled visit will be imputed, separately for each treatment group, under the MAR assumption using a multivariate normal imputation model and the Markov Chain Monte Carlo (MCMC) method with multiple chains. The number of imputations will be 40. The resulting data will have a monotone missing data pattern. The imputed data will be used together with the observed data to impute post discontinuation missing values.

Step 1 (b)

Only after Step 1a is completed, the remaining monotone missing data after discontinuation will be imputed using the FCS predictive mean matching method based on data from the

placebo group only. The RB, SF, ES, and PGA subscores, stratification variables, a binary variable indicating if a participant is a treatment failure, and biomarker measurements (ALC, FCP, hs-CRP, log-transformed) at each planned visit will be included in the imputation model.

Step 2

Same as Step 2 described in Section 5.3.1.2.1 above.

Step 3

Same as Step 3 described in Section 5.3.1.2.1 above.

Step 4

Same as Step 4 described in Section 5.3.1.2.1 above.

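### Copy Reference in SAP 5.3.1.2.3 contradicts its own opening rule and, followed step by step, leaves the analysis labelled MNAR with essentially no MNAR content

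*SAP*

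**What the plan says.** SAP 5.3.1 names four sensitivity methods for participants whose binary outcome is missing: multiple imputation under MAR, a tipping-point analysis, Copy Reference under MNAR, and a hybrid. SAP 6.1, Table 6, applies all four to the primary and the eight key secondary endpoints, in the Primary Analysis Set.

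**Copy Reference (SAP 5.3.1.2.3).** The opening paragraph states that "each missing value of MMS subscores for participants in the treatment group will be imputed using observed MMS subscores in the placebo group"; placebo gaps are imputed under MAR. Step 1(a) then imputes intermittent gaps arising before a participant leaves the study, in each arm separately and under MAR. Step 1(b) imputes what is left after discontinuation, using placebo data only, without naming the arm or participants concerned. Its model lists RB, SF, ES, PGA, strata, a treatment-failure flag and the biomarkers. Geboes is not in it.

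**What counts as missing.** SAP 2.2.3 and 5.3.1.1 make discontinuation of study treatment for any reason an intercurrent event with a known nonresponse. Only measurements missing for other reasons stay missing. Protocol 10.4 differed: discontinuation for reasons other than worsening disease or a UC-related adverse event was missing data, and Copy Reference was meant for outcomes after discontinuation.

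**The MAR model (SAP 5.3.1.2.1).** "A separate imputation model will be used for each treatment group". The method "will be used to impute the missing data at all timepoints". RB, SF, ES, PGA, strata, a flag for prior failure of oral 5-ASA only, Geboes and "biomarker measurements (absolute lymphocyte count [ALC], fecal calprotectin [FCP], hs-CRP, log-transformed) at each planned visit will be included in the imputation models". The hybrid analysis (SAP 5.3.1.2.4) reuses this model.

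**The concern.** Copy Reference is there to show what happens if etrasimod participants with missing outcomes behave like placebo participants. If its steps impute those participants from their own arm, or do not reach them, it largely repeats the MAR analysis. Agreement between the two would then carry little information, and two programmers could follow the same section to different results.

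The Copy Reference steps fit the protocol's definition of missing data better than the SAP's. SAP Section 1, Table 1, records that version 3.0 changed the intercurrent event in 2.2.3, 2.2.4 and 5.3.1.1. The changes it lists for 5.3.1.2 are random seeds and the Ukraine-war addition to the hybrid method.

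A second, smaller matter is that the visits entering the per-arm imputation model are not stated, and the placebo arm is small.

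**Working it through.** **1. Which rule reaches which missing etrasimod value**

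| Missing etrasimod value | Opening rule | Steps 1(a)/1(b) | Status under SAP 2.2.3 and 5.3.1.1 |
|---|---|---|---|
| Gap with later data, still in study | from placebo | own arm, MAR | missing |
| Missed Week 52 endoscopy, on treatment to the end | from placebo | own arm, MAR, if read as before study discontinuation; neither step if intermittent means followed by later data | missing |
| After leaving the study during the treatment period | from placebo | from placebo | known nonresponse, since treatment has stopped |

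The steps use placebo data only in the last row, where the outcome is not missing. In the two rows where it is missing, they either contradict the opening rule or are silent.

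**2. Size of the difference.** The documents give no missing rates, so these are assumed. Take 34% and 14% (SAP 2.3) as the rates with missing counted as nonresponse, and let a fraction m of each arm be on treatment with a missing Week 52 outcome. The observed rates are 0.34/(1−m) and 0.14/(1−m).

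- Within-arm MAR: difference = 0.34/(1−m) − 0.14/(1−m).
  - m = 5%: 35.8 − 14.7 = 21.1 points
  - m = 10%: 37.8 − 15.6 = 22.2 points
  - m = 15%: 40.0 − 16.5 = 23.5 points
- Etrasimod from placebo, with q = 0.14/(1−m): difference = 0.34 + m·q − q = 0.34 − (1−m)q = 0.34 − 0.14 = 20.0 points at every m. Example, m = 10%: 0.34 + 0.1 × 0.1556 − 0.1556 = 0.200.

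The gap is 1.1, 2.2 and 3.5 points. This ignores covariates and assumes equal missing rates in the two arms.

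**3. Geboes.** Histologic-Endoscopic Mucosal Improvement (SAP 3.2.1) needs both ES and Geboes. Table 6 gives it the same sensitivity methods as the primary endpoint, so Copy Reference must impute Geboes with a model that does not contain it.

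**4. Predictor count in placebo**

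- *Planned number.* SAP 2.3: "approximately 183 subjects (122 etrasimod, 61 placebo) are required". At 34% versus 14% with 122/61, exact Fisher power is 81.0% (0.025 in the upper tail) or 83.8% (minimum-likelihood p-value), so the stated 80% reproduces. From enrolment, 225 − 45 = 180, and 180/3 = 60 placebo. The planned placebo set is therefore about 60-61.
- *Visits, counting baseline.* RB and SF 11 each (SAP 3.4.1: "Symptomatic remission at each study visit (Weeks 2, 4, 8, 12, 16, 24, 32, 40, 48, and 52"); ES, PGA and Geboes 3 each (protocol 9.8.2.1, 9.8.2.2 and Table 6); ALC and hs-CRP 10 each and FCP 7 (SAP 3.4.3; for FCP, "Change from baseline in level of fecal calprotectin at Weeks 2, 4, 8, 12, 24, and 52"); two strata and one 5-ASA flag.
- *Widest reading:* 22 + 3 + 3 + 3 + 10 + 10 + 7 + 3 = 61.
- *RB and SF only at baseline, Week 12 and Week 52:* 6 + 3 + 3 + 3 + 10 + 10 + 7 + 3 = 45.
- *All eight measures only at those visits:* 8 × 3 + 3 = 27.

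Each regression has (variables − 1) predictors and an intercept, so residual df = observed n − variables. With 60 placebo participants and an assumed 0/10/20/30% missing (n = 60/54/48/42):

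| Variables | Placebo residual df |
|---|---|
| 61 | −1 / −7 / −13 / −19 |
| 45 | 15 / 9 / 3 / −3 |
| 27 | 33 / 27 / 21 / 15 |

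With 61 participants the widest reading has 0 df before anything is missing. The Copy Reference list, without Geboes, has 58, 42 or 24 variables on the same three readings.

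An illustrative simulation (invented data model, arms of 120 and 60, 20 imputations, five nearest donors) could not fit the 61-variable placebo model at 10% or 20% missing. Among readings that could be fitted, the choice moved the pooled difference by at most about 1.3 points, or 1.7 in a run with higher remission rates.

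**The case against.** The strongest reply is that little depends on this. The primary analysis counts all missing data as nonresponse, and neither reading in step 2 falls below its 20.0 points. That stands, and it limits the severity.

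Three stronger readings might be inferred, and the documents do not support them.

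- *That departures from MAR go untested.* The tipping-point analysis (SAP 5.3.1.2.2) varies the response probability among missing participants independently by arm, for example up to 0.3 in placebo and from 0.0 to 0.5 in etrasimod. That range includes equal probabilities, which is the placebo-like case, and worse ones for etrasimod.
- *That Step 1(b) imputes discontinuers and so changes the estimand.* SAP 5.3.1 applies these methods to missing outcomes, and 2.2.3 and 5.3.1.1 give discontinuers a known one. Step 1(b) simply has no effect on those outcomes.
- *That the MAR imputation cannot be run.* This is true only of the widest reading. SAP 5.3.1.2.1 says the method allows a separate conditional distribution for each variable, and its Step 2 classifies responders only at Weeks 12 and 52. The planned numbers are approximate: "these participants will be excluded from the Primary Analysis Set (Section 4). Therefore, approximately 225 total participants (150 etrasimod, 75 placebo".

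It can also be said that a participant still in the study who misses the Week 52 endoscopy fits Step 1(a). That is a fair reading, but it puts this participant under within-arm MAR, which is the defect described. On Geboes, 5.3.1.2.3 speaks of endpoints based on MMS; the mismatch with Table 6 remains, though it is small.

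**Conclusion.** The point holds as an internal contradiction in one sensitivity analysis. The opening rule of SAP 5.3.1.2.3 and its Steps 1(a) and 1(b) cannot both be followed for etrasimod participants without an intercurrent event. Followed by its steps, the analysis has essentially no MNAR element. Under the assumed 5-15% missing, the two rules differ by 1.1 to 3.5 points on a planned difference of 20. Those sizes rest on the assumed missing rates, on equality between arms and on marginal rates; the contradiction itself rests on the text alone.

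The omission of Geboes affects one key secondary endpoint under Copy Reference. The unstated predictor visits in 5.3.1.2.1, which also affect the hybrid analysis, are a prespecification gap and not evidence of material bias. Severity is minor.

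**What to change.** Before unblinding:

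1. Rewrite Steps 1(a) and 1(b) of SAP 5.3.1.2.3 so that missing etrasimod values at the endpoint visits, in participants without an intercurrent event, are imputed from placebo. State that intercurrent events 1-4 remain nonresponse.
2. Add Geboes to the Copy Reference model.
3. In SAP 5.3.1.2.1, state which visits supply predictors (for example baseline, Week 12 and Week 52 for all eight measures, giving 27 variables), and give an order for dropping predictors if a model cannot be fitted. Apply the same statement to Copy Reference and the hybrid method.

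The cost is SAP wording and some programming, with no new data. The downside of item 3 is fewer auxiliary variables supporting MAR. Adding RB and SF at Week 48 would recover part of that: 29 variables leave placebo df of 31/25/19/13 at 0/10/20/30% missing.
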